#### 4.3.9 Main Study Assessment: Xerostomia Questionnaire

Patients in this study will be asked to complete the Xerostomia Questionnaire and two additional supplemental survey questions at baseline (prior to radiation in randomized patients and within 5

days of radiation initiation in patients refusing randomization but consenting for the observation arm), at the end of radiation (on or within 5 days after the final day of radiation), then at two weeks (+/- 5 days) and one, three, and six months (+/- 7 days) after radiation completion, for a total of six planned surveys. This survey may be administered by phone or by email, vs. in person if the patient has an appointment at the appropriate time point necessary for clinical follow-up. This survey also acts as the screening questionnaire completed by patients prior to enrollment, and counts as the baseline questionnaire for those consenting to enrollment.

The full survey (see appendix) will consist of the validated University of Michigan Xerostomia Questionnaire (questions 1-8) and two additional questions related to dry mouth, (questions 9-10). Questions 1-8 will be answered on a Likert scale ranging from 0 (least bothersome) to 10 (most bothersome), summed, and linearly converted to a scale from 0-100. Questions 9-10 will be answered on a Likert scale with four responses: Not at all, a little, quite a bit, and very much. Questions 9-10 are designed to quantify the overall importance of dry mouth symptoms to each patient, and were adapted from the validated EORTC QLQ-H&N35 head and neck specific questionnaire [17].

#### **4.3.10 Other Assessments**

At the initial / baseline assessment, patients' Eastern Cooperative Oncology Group (ECOG) performance status will be recorded. Relevant demographic and clinical data will be abstracted from the medical record as part of this study. For patients randomized to standard WBRT, the parotids will be delineated retrospectively for dosimetric analysis. For patients randomized to parotid sparing WBRT, the parotids are prospectively delineated and dosimetric data prospectively collected.

For the purposes of assessing factors potentially confounding the measurement of dry mouth, we will prospectively record at the baseline assessment whether patients are taking different classes of medications. At the end of RT time point. We will record whether the patients required steroids at any point during radiation. At the 1 month time point, we will also record whether the patient has received systemic therapy (including chemotherapy) after WBRT. The details of these assessments are found in section 5.1 (Time and Events Table).

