#### **4.3.1 Screening for Eligibility and Registration Details**

Patients identified as qualifying for the trial will be divided into those who were identified prior to radiation start vs. those identified after radiation start. Patients interested in participating will complete an anonymous screening baseline xerostomia questionnaire identical to the primary study assessment (see Section 4.3.9, below). Patients scoring  $\geq 40$  pts on the screening xerostomia questionnaire are ineligible. Patients scoring  $< 40 / 80$  will be eligible and offered enrollment on the study. Questionnaires completed by patients who are found to be ineligible or who decline to enroll on the study will be destroyed. Questionnaires completed by patients who consent to the trial will be assigned patient information (de-anonymized) and serve as their baseline quality of life data.

Patients identified prior to radiation start will be offered enrollment into the randomization arms (Consent form 1, arms A and B), with the observation arm (Consent form 2, arm C) offered to those who refuse randomization. Patients identified after radiation has already started, but within 5 days of the first day of radiation, will be offered enrollment into the observational arm (Consent form 2, arm C).

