## **5.0 TIME AND EVENTS TABLE**

### **5.1 Time and Events Table**

	Pre-study / Baseline 	Radiation	End-RT 	2 Weeks Post-RT 	1 Month Post-RT 	3 Months Post-RT 	6 Months Post-RT 
Informed Consent	x						
Xerostomia Questionnaire	x		x	x	x	x	x
ECOG Performance Status Assessment	x						
Steroid Assessment 	x		x				
Narcotic Assessment 	x						
Anticholinergic Assessment 	x						
Systemic Therapy Assessment 					x		
Quality Assurance (1 st 4 pts per site)			x				
Medical Record Abstraction		Continuously throughout study					

1. For randomized group this should be completed before treatment start, but no more than 30 days before treatment start. The observational arm should within 30 days of treatment start and up to 5 days after the first fraction of radiation is delivered.
2. This should be completed on the last day of treatment or up to 5 days after treatment end.
3. +/- 5 days
4. +/- 7 days
5. Is the patient on or has the patient been prescribed a steroid medication (eg, dexamethasone, methylprednisolone, or prednisone)? (Yes vs. No)
6. Is the patient on or has the patient been prescribed a narcotic medication (eg, hydrocodone, oxycodone, morphine, dilaudid, or fentanyl)? (Yes vs. No)
7. Is the patient on or has the patient been prescribed an anticholinergic medication on the following list? (Yes vs. No)
  - a. Amitriptyline (Elavil)

- b. Meclizine (Antivert)
- c. Prochlorperazine (Compazine)
- d. Scopolamine (Transderm Scop)
- e. Hydroxyzine (Atarax)
- f. Benztropine (Cogentin)
- g. Chlorpromazine (Thorazine)
- h. Olanzapine (Zyprexa)
- i. Quetiapine (Seroquel)
- j. Dicyclomine (Bentyl)
- k. Atropine (Donnatal)
- l. Oxybutynin (Ditropan)
- m. Solifenacin (Vesicare)
- n. Tolterodine (Detrol)
- o. Cyclobenzaprine (Flexeril)

8. Has the patient received any systemic chemotherapy, immunotherapy, or targeted therapy between WBRT and the time of the 1M assessment? (Yes vs. No)

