### **7.3 Data Analysis Plans**

The primary data analysis plan is to compare the proportion of patients in each randomization arm experiencing a  $\geq 15$  point xerostomia score increase between baseline and 1 month, with the use of a two group chi-square test. As sample size allows, linear mixed effects models will be explored to evaluate changes over time including all repeated measurements. It is anticipated that a significant number of enrolled patients will be unable to complete the 3 month (estimated 40% response rate) and 6 month (estimated 20% response rate) post-radiation questionnaires due to disease morbidity and mortality, so modeling may be limited to the earlier time points. In such a

scenario with significant patient dropout, separate analyses will be performed for patients with vs. without long term follow up.

Descriptive statistics will be provided for all scores at all time-points and to summarize the patient population. Secondary data analyses will estimate the time to marginal relapse (defined as within 1 cm of the block edge overlying the blocked parotids) and the time to upper cervical spine relapse (defined as relapses in the C1 or C2 vertebrae) in each randomization arm using the Kaplan Meier method. A log rank test will be used to compare these time to event outcomes. Furthermore, the above analyses exploring xerostomia will also be conducted in all patients (including those who refused randomization but consented for the observational arm).

A linear regression model will be used to further explore the dosimetric relationship between parotid dose and xerostomia, to supplement data from LCCC 1540.

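### Drug use is recorded to assess confounding of dry mouth, but Section 7.3 names no adjustment in the all-patient comparison or the dose regression, which randomization does not protect

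*Combined protocol and SAP*

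**What the plan says.** Section 4.3.10 gives the reason for recording drug use: "For the purposes of assessing factors potentially confounding the measurement of dry mouth, we will prospectively record at the baseline assessment" which medication classes patients take. It adds two later items: "We will record whether the patients required steroids at any point during radiation", and "At the 1 month time point, we will also record whether the patient has received systemic therapy (including chemotherapy) after WBRT".

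The Time and Events Table (5.1) sets the timing. The narcotic item ("Is the patient on or has the patient been prescribed a narcotic medication") and the anticholinergic item ("Is the patient on or has the patient been prescribed an anticholinergic medication on the following list") are marked at baseline only. Steroids are marked at baseline and End-RT, and systemic therapy at 1 month.

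The screening questionnaire answers of consenting patients "serve as their baseline quality of life data" (4.3.1), and the primary endpoint (2.4) is a rise of at least 15 points from there to 1 month.

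Section 7.3 plans a two-group chi-square test, mixed models if the sample size allows, a repeat of the xerostomia analyses in all patients including the observational arm, and this: "A linear regression model will be used to further explore the dosimetric relationship between parotid dose and xerostomia". None of these names a covariate. In Arm C the treating physician chooses standard or parotid sparing fields (4.3.7).

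**The concern.** The protocol identifies possible confounders, collects them, and then gives them no stated role in the readable analysis text. In a randomized comparison that costs little. Secondary endpoint #2, however, pools randomized patients with Arm C, where field type is the physician's choice and baseline may be taken up to 5 days after treatment starts. If physicians, sites or sicker patients differ both in field type and in use of drying drugs, the pooled comparison mixes the two effects. The dose regression has the same weakness, because parotid dose within an arm is not randomly assigned.

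Two further gaps are smaller. A fixed 15-point rise depends on the starting score, yet no analysis adjusts for it. And no steroid, narcotic or anticholinergic question coincides with the 1-month endpoint.

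**Working it through.** **1. The plan's own figure.** Inputs from Section 7.2: 42% versus 14%, one-sided 0.05, 80% power. With mean proportion 0.28:

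n = [1.645 × √(2 × 0.28 × 0.72) + 0.8416 × √(0.42 × 0.58 + 0.14 × 0.86)]² / 0.28² = (1.0445 + 0.5078)² / 0.0784 = 30.7, so 31 per arm.

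Power at 31 is 80.3%. Enrolment is 62 / 0.70 = 88.6, so 89, against 90 stated. The sample size reproduces and is not in question.

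**2. Schedule (4.3.10 and 5.1).**

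| Factor | Baseline | End-RT | 1 month |
|---|---|---|---|
| Steroids | yes | yes | no |
| Narcotics | yes | no | no |
| Anticholinergics | yes | no | no |
| Systemic therapy | no | no | yes |

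Two of the four factors are asked about at baseline only. None of the three medication classes is asked about at 1 month.

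**3. Analyses (7.3).**

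| Xerostomia analysis | Protected by randomization | Covariates named |
|---|---|---|
| Chi-square, Arms A and B | yes | none |
| Mixed models | yes, in Arms A and B | none |
| Same analyses, all patients | no | none |
| Dose regression | no | none |

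**4. Possible bias without randomization.** The documents give no rate of drug-caused rises, so this is illustration only. Let r be the radiation-caused rate of a rise of at least 15 points, and q the independent drug-caused rate. The observed rate is r + (1 − r)q. Assume r = 30% in both field groups, so that there is no true difference.

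- q = 10% versus 20%: 0.30 + 0.70 × 0.10 = 37%; 0.30 + 0.70 × 0.20 = 44%. False difference: 7 points.
- q = 5% versus 20%: 33.5% versus 44%. False difference: 10.5 points.
- q = 10% in both: 37% each. No false difference.

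Bias therefore requires drug use to differ between the field groups.

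**5. Randomized comparison.** Equal q in both arms leaves equal rates under the null, so type I error is preserved. Chance imbalance remains. If a share m of patients starts a drying drug, the SD of the between-arm difference is √(2m(1 − m)/31): 10 percentage points at m = 20% and 12 at m = 40% (assumed shares).

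**6. Baseline score as covariate.** Entry below 40/80 allows at most 39 / 0.8 = 48.75 on the 100-point scale. A simulation used 31 per arm, rates of 42% and 14% from a latent-normal model, a linear model with robust (HC3) errors, and one-sided 0.05. With an assumed baseline-change correlation of -0.4 to -0.6, adjustment moved power from about 82% to 82-86%. At -0.3 there was no gain. A yes/no drug covariate alone (assumed 0.5 SD effect, 40% prevalence) also gave none. Type I error stayed close to 5%.

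**The case against.** A reader might infer several stronger things, which the documents do not support.

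- *Drug-caused rises bias or undermine the primary test.* Randomization balances them in expectation. One can calculate that if drugs cause a rise in 5-10% of patients, the planned drop requires sparing to prevent 76-88% of radiation-caused events rather than 1 − 14/42 = 67%. At 5%: 1 − 0.58/0.95 = 38.9% and 1 − 0.86/0.95 = 9.5%, a 76% reduction. But the drug rate is assumed. The 42% was observed after routine WBRT, so it already contains any such rises. The endpoint also counts clinically significant xerostomia whatever its cause.
- *The baseline score is unused.* It is subtracted in the endpoint and is one of the repeated measurements in the mixed models. Only its use as a covariate is missing.
- *Drugs started later are never recorded.* Section 4.3.10 says: "Relevant demographic and clinical data will be abstracted from the medical record as part of this study". Table 5.1 runs abstraction throughout the study. No drug fields or dates are specified, so recovery is neither assured nor excluded.
- *No planned analysis uses the drug items.* The exploratory objectives and endpoints are redacted, and the descriptive statistics in 7.3 may include the items. Only the readable text can be judged.

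Two further objections stand. The affected analyses are secondary or supplementary. And a drug started after planning cannot have determined parotid dose, so baseline values are the right adjusters and drug use at 1 month is post-exposure. Neither explains why baseline items collected to assess confounding have no named role in the analyses that need them.

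**Conclusion.** The point holds for the unprotected analyses. As written, the all-patient comparison and the dose regression would be run with no named adjustment, although relevant baseline values are already collected. The size of any bias cannot be calculated: the documents give neither the rate of drug-caused rises, nor the drug use by field type, nor the number of Arm C patients. The 7 to 10.5 points above rest wholly on assumed rates.

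For the randomized comparison the finding is modest: possible loss of precision and chance imbalance, with type I error intact. The simulated gain, from about 82% to at most 86%, comes from the baseline score and depends on an assumed correlation of -0.4 to -0.6. It should not be read as a benefit of adjusting for drugs. The missing 1-month drug questions limit description and sensitivity analysis; they do not invalidate the endpoint.

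**What to change.** 1. In Section 7.3, adjust the all-patient comparison and the dose-xerostomia regression for baseline xerostomia score, the baseline steroid, narcotic and anticholinergic items, and ECOG status. In the all-patient analysis add randomized versus observational enrolment. This reduces confounding through measured baseline factors only, and the report should say so.
2. Keep the chi-square test and add a baseline-score-adjusted risk difference for the randomized 1-month comparison, with robust standard errors or standardization.
3. Optionally, repeat the three yes/no medication items in 5.1 at the 1-month survey, worded as current use, because the present items merge current use with past prescription. Use the answers only descriptively and in sensitivity analyses, since they are post-exposure.

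Items 1 and 2 need only analysis wording, because the data are already collected. Item 3 adds three yes/no questions to an existing contact. The downside is slight extra data entry and analysis, with little gain if the covariates prove weakly prognostic. Treatment and sample size do not change.

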#### **4.3.11 Follow Up**

Follow up for the purposes of this study is limited to the administration of surveys up to six months post-radiation, which is the last planned questionnaire. Participation in this study will not impact the actual clinical follow-up schedule of patients receiving WBRT, which is based on the discretion of the treating radiation oncologist. Although a secondary endpoint is the rate of marginal relapse around the blocked parotid glands, this will be assessed using data obtained as part of standard of care follow-up of these patients. No additional visits or protocol-specified imaging will be required, as this would unnecessarily burden these palliatively treated patients, given the minimal expectation that a meaningful difference in tumor control exists (see section below on expected risks).

### **4.4 Expected Risks**

Patients randomized to standard WBRT will not be subject to any risks specific to participation in this trial; these patients receive standard treatment and simply complete the study assessment at post-treatment time points. Several theoretic risks warrant mention for patients randomized to parotid sparing WBRT:

1. By delineating and minimizing dose to the parotids, the target (brain) could receive a lower dose, which could place the patient at higher risk of inferior brain relapse.
2. By omitting coverage of C1/C2, patients may develop bony metastases in this location which may be more difficult to treat with radiation in the future, given the abutment of the prior parotid sparing field.

For the following reasons, these risks are minimal:

1. The standard field arrangements of WBRT covering the upper cervical vertebrae have become standard practice with the advent of CT-based planning. Prior to CT-based planning, WBRT was delivered with an angled rectangular field splitting the cervical vertebrae. With the use of CT-based planning, WBRT fields became horizontal, and coverage of the cervical vertebrae was added to provide an additional margin around the foramen magnum. However, our preliminary analysis of LCCC 1540 and other studies [15, 18] show that coverage of brain is minimally affected with alterations to the field to maximize sparing of the parotids. Some of these studies have done this by omitting the upper cervical vertebrae and others have simply reduced the field borders in areas overlapping with the parotids. Therefore, target coverage is not expected to be compromised.
2. Regardless of any reductions in field size and the negligible impact on dose to the brain described above, whole brain radiation is essentially treatment of mostly subclinical disease in addition to areas of actual brain metastases. However, the field of radiation oncology as a whole has generally accepted that treatment of subclinical disease in the brain is not strictly necessary. This is demonstrated by the increasing use of stereotactic radiosurgery for multiple brain metastases with *no* elective brain treatment; it is generally accepted that if these patients develop new brain metastases they can be salvaged with additional stereotactic radiosurgery. Therefore, a small margin reduction with the goal of improving patient quality of life in a population with limited life expectancy should be acceptable and entail minimal excess risk.
3. For the same reason as above, omission of the C1/C2 vertebrae should also be of minimal significance. Given the overall poor prognosis of patients receiving WBRT, the rate of significant marginal bony relapses adjacent to the inferior WBRT field is expected to be extremely low. Furthermore, with the advent of stereotactic radiosurgery, any such relapses would still be safely treatable with definitive or palliative intent.
4. Finally, the willingness of many physicians and several institutions [1, 18-20] to adopt parotid sparing WBRT as their *current standard* is a testament to the generally low risk involved.

#### **4.5 Removal of Patients from Protocol**

Patients will be informed that they can request to withdraw from participation in this study at any time. If a patient withdraws from the study, they will no longer be contacted for the purposes of collecting data related to this study.

## **5.0 TIME AND EVENTS TABLE**

### **5.1 Time and Events Table**

	Pre-study / Baseline 	Radiation	End-RT 	2 Weeks Post-RT 	1 Month Post-RT 	3 Months Post-RT 	6 Months Post-RT 
Informed Consent	x						
Xerostomia Questionnaire	x		x	x	x	x	x
ECOG Performance Status Assessment	x						
Steroid Assessment 	x		x				
Narcotic Assessment 	x						
Anticholinergic Assessment 	x						
Systemic Therapy Assessment 					x		
Quality Assurance (1 st 4 pts per site)			x				
Medical Record Abstraction		Continuously throughout study					

1. For randomized group this should be completed before treatment start, but no more than 30 days before treatment start. The observational arm should within 30 days of treatment start and up to 5 days after the first fraction of radiation is delivered.
2. This should be completed on the last day of treatment or up to 5 days after treatment end.
3. +/- 5 days
4. +/- 7 days
5. Is the patient on or has the patient been prescribed a steroid medication (eg, dexamethasone, methylprednisolone, or prednisone)? (Yes vs. No)
6. Is the patient on or has the patient been prescribed a narcotic medication (eg, hydrocodone, oxycodone, morphine, dilaudid, or fentanyl)? (Yes vs. No)
7. Is the patient on or has the patient been prescribed an anticholinergic medication on the following list? (Yes vs. No)
  - a. Amitriptyline (Elavil)

- b. Meclizine (Antivert)
- c. Prochlorperazine (Compazine)
- d. Scopolamine (Transderm Scop)
- e. Hydroxyzine (Atarax)
- f. Benztropine (Cogentin)
- g. Chlorpromazine (Thorazine)
- h. Olanzapine (Zyprexa)
- i. Quetiapine (Seroquel)
- j. Dicyclomine (Bentyl)
- k. Atropine (Donnatal)
- l. Oxybutynin (Ditropan)
- m. Solifenacin (Vesicare)
- n. Tolterodine (Detrol)
- o. Cyclobenzaprine (Flexeril)

8. Has the patient received any systemic chemotherapy, immunotherapy, or targeted therapy between WBRT and the time of the 1M assessment? (Yes vs. No)

## **6.0 UNANTICIPATED PROBLEMS**

### **6.1. Definition**

As defined by UNC's IRB, unanticipated problems involving risks to study subjects or others (UPIRSO) refers to any incident, experience, or outcome that:

- Is unexpected (in terms of nature, severity, or frequency) given (a) the research procedures that are described in the protocol-related documents, such as the IRB-approved research protocol and informed consent document; and (b) the characteristics of the subject population being studied;
- Is related or possibly related to a subject's participation in the research; and
- Suggests that the research places subjects or others at a greater risk of harm (including physical, psychological, economic, or social harm) related to the research than was previously known or recognized.

### **6.2. Reporting**

Any UPIRSO that occurs during the conduct of this study and that meets all three criteria listed in 6.1 must be reported to the UNC IRB using the IRB's web-based reporting system.

### **6.3 Monitoring and Oversight**

The Principal Investigator will provide continuous monitoring of patient safety in this trial with periodic reporting to the Data and Safety Monitoring Committee (DSMC) as required. This will include UNC and affiliate sites.

Meetings/teleconferences will be held at a frequency dependent upon study accrual and in consultation with the study Biostatistician. At these meetings, the research team will discuss all

issues relevant to study progress, including enrollment, safety, regulatory, data collection, etc. and the team will produce summaries or minutes of these meetings.

